Endoscopic sinus surgery (ESS) to change quality of life for adults with recurrent rhinosinusitis

Statistical analysis plan

04.09.2020

Statistical methods for primary and secondary outcomes

To describe the data the following methods will be used. Data for normal distribution will be presented as mean and standard deviation (SD). Variables for skewed distributions will be described as median and interquartile range. Categorical variables will be expressed as frequencies with percentages.

The primary and secondary outcomes, measures and planned statistical analyses are displayed in Table 2. Our primary outcome is the difference between the average change in SNOT-22 scores from baseline to six months between the ESS and control groups. If the average baseline scores happen to be different between the two groups, comparison of the follow-up scores or change scores will lead to under- or overestimation of the treatment effect. Therefore, the analysis of covariance will be used where possible baseline imbalances are controlled for. The estimate for difference between the means will be calculated with 95% confidence intervals. Statistical significance will not be presented for secondary outcomes to avoid multicomparison problem.

Table 2. Variables, measures and planned statistical analyses. ESS= endoscopic sinus surgery, SNOT-22= Sinonasal outcome test quality of life questionnaire, RAND 36 = Research and Development 36 Item Health Survey, MIC = minimal clinically important change, CI = confidence interval, NNT= number needed to treat

Variable/Outcome	Hypothesis	Outcome measure	Method of analysis
------------------	------------	-----------------	--------------------

Primary outcome	ESS improves outcome from baseline to 6 months	Difference between the mean SNOT-22 change scores of ESS and control group	Analysis of covariance, estimate for difference between means with 95% CI (adjusted age (≤ 50 vs. > 50 years), sex and allergy status (yes vs, no))
Secondary outcomes			
General QoL change	Improvement occurs	Difference between the mean RAND-36 change scores of ESS and control group	Analysis of covariance
Proportion benefiting	Improvement occurs	Difference in proportions benefiting (SNOT-22 $>$ MIC) in ESS and control group	Chi-squared test, Risk ratio with 95% CI, NNT

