No. of episodes, visits, antibiotic courses, sick days	Improvement occurs	Difference in number of episodes, visits, antibiotic courses and sick days in ESS and control group	Difference in means with 95% CI
No. of symptomatic days	Improvement occurs	Difference in no. of days with nasal obstruction, nasal discharge, facial pain/pressure, and fever in ESS and control group	Difference in means with 95% CI
No. of postoperative complications	Improvement occurs	Frequency of postoperative synechia formations, infections, nasal pain, bleeding,	Number (%)

and orbital and
intracranial
complications

Methods for additional analyses (e.g. subgroup and adjusted analyses)

We plan to conduct two subgroup analyses. We know that both age and sex will probably affect quality of life and medical care seeking. Firstly, we will compare the estimates for difference between the mean SNOT-22 scores between the ESS and control groups both in males and females. Secondly, we will do the same analysis in participants aged ≤ 50 and > 50 years of age. We anticipate that the treatment effect will be larger among both females and younger participants.

If there is imbalance in baseline variables (age, sex, allergy status) between groups, we also perform adjusted analyses by including the following baseline variables in the analysis of covariance: age (≤ 50 vs. > 50 years), sex, and allergy status (yes vs. no).

Methods in analysis to handle protocol non-adherence and any statistical methods to handle missing data

An “as randomised” analysis is performed which retains participants in the group to which they were originally allocated (intention to treat principle). Outcome data obtained from all participants are included in the data analysis, regardless of protocol adherence. Per protocol analysis will be performed as sensitivity analysis. In case there is missing data on the primary outcome, a multiple imputation method will be used.

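### Age, sex and allergy are pre-specified as covariates for SNOT-22 only: RAND-36 gets them through an undefined imbalance trigger, and the care-use and symptom-day outcomes not at all (minor)

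*SAP*

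**What the plan says.** Four places in the SAP bear on this.

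- **Table 2, primary outcome row.** SNOT-22 change is analysed by analysis of covariance, "adjusted age (≤ 50 vs. > 50 years), sex and allergy status (yes vs, no"). No condition is attached.
- **Table 2, general quality-of-life row.** The outcome is "Difference between the mean RAND-36 change scores of ESS and control group". The method cell says analysis of covariance and names no covariate.
- **Table 2, rows for care use and for symptomatic days.** The method in both is "Difference in means with 95% CI". The proportion benefiting is likewise unadjusted: "Chi-squared test, Risk ratio with 95% CI, NNT".
- **Methods for additional analyses.** The subgroup paragraph gives as its reason "We know that both age and sex will probably affect quality of life and medical care seeking". The next paragraph sets the only other adjustment rule: "If there is imbalance in baseline variables (age, sex, allergy status) between groups, we also perform adjusted analyses", to be done "by including the following baseline variables in the analysis of covariance". It gives no threshold for imbalance and names no outcome.

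**The concern.** The SAP expects age and sex to matter for two domains, quality of life and care seeking. RAND-36 is its general quality-of-life outcome, and visits and antibiotic courses are its outcomes closest to care seeking. Those rows do not carry the covariates that the SNOT-22 row carries. For RAND-36 the decision is left to a judgement of imbalance that can be made once the data are visible. For the care-use and symptom-day rows, the SAP accepts in principle that imbalance calls for adjustment but words the remedy so that it cannot apply to them.

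Two things are at stake: precision in the secondary estimates, which the SAP reports without significance statements and which therefore rest on their intervals, and a data-dependent choice about how RAND-36 is analysed.

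**Working it through.** The SAP gives no sample size, standard deviation, effect size or randomisation method, so there is no figure of its own to reproduce. The main check sets the text side by side. The arithmetic after it only shows scale.

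**1. Which outcomes can receive the three covariates**

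- SNOT-22: yes, unconditionally (Table 2). The additional-analyses rule also covers it, since it too is analysed by covariance. Under that rule adjustment is an extra step taken on imbalance, which implies an unadjusted main analysis. The two passages disagree.
- RAND-36: none named in Table 2. The rule covers it because the method is analysis of covariance. That it gets the covariates only on imbalance is the natural reading, not an explicit statement.
- Visits, episodes, sick days, antibiotic courses, symptomatic days: none named, and the rule cannot reach them because they have no analysis of covariance.
- Proportion benefiting: none named, and out of reach for the same reason.

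**2. Precision given up by not adjusting**

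For a linear model whose covariates explain a share R² of outcome variance, the ratio of adjusted to unadjusted interval width is √(1 − R²). The equivalent gain in sample size is 1/(1 − R²) − 1. R² is assumed.

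- R² = 0.02: √0.98 = 0.990, so 1.0% narrower; equivalent to 2.0% more participants.
- R² = 0.05: √0.95 = 0.975, so 2.5% narrower; equivalent to 5.3% more.
- R² = 0.10: √0.90 = 0.949, so 5.1% narrower; equivalent to 11.1% more.
- R² = 0.20: √0.80 = 0.894, so 10.6% narrower; equivalent to 25.0% more.

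**3. How far a chance imbalance moves an unadjusted difference**

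If one covariate carries the whole R², a 1-SD chance imbalance moves the unadjusted difference by √R² of its own standard error: √0.05 = 0.22 and √0.10 = 0.32. The unadjusted standard error already contains this variation.

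**4. How often an imbalance check might fire by chance**

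The SAP gives no criterion. Suppose it meant a p-value below a cut-off a on any of three independent covariates. The chance of triggering is 1 − (1 − a)³:

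- a = 0.05: 1 − 0.95³ = 0.143
- a = 0.10: 1 − 0.90³ = 0.271
- a = 0.20: 1 − 0.80³ = 0.488

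Depending on a cut-off nobody has fixed, the adjusted RAND-36 analysis would appear in roughly 14% to 49% of trials through chance alone.

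**The case against.** The strongest reply is that leaving secondary outcomes unadjusted is a legitimate choice. A reader might infer that a chance difference in sex or age mix biases the RAND-36 and care-use results, or that disagreement between SNOT-22 and the secondary outcomes could be an artefact of unequal adjustment. The SAP does not support either inference. Under randomisation the unadjusted difference in means is unbiased, its 95% interval already allows for chance imbalance, and adjusted and unadjusted estimators of a difference in means target the same quantity. This part of the reply stands in full.

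Other parts also stand:

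- The sentence on age and sex is hedged with *probably*, is offered as the reason for two SNOT-22 subgroup analyses, and does not mention allergy. It is not a commitment to adjust. The case for allergy rests only on its place in the primary row and in the imbalance rule.
- Every magnitude is assumed. Stratified randomisation on these factors, which the SAP does not describe, would make imbalance rarer than step 4 suggests.
- The conflict over whether the primary analysis is adjusted unconditionally matters more than the treatment of the secondary outcomes.
- The proportion benefiting is unadjusted too, so a repair limited to differences in means does not make adjustment uniform.

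What the reply does not remove: RAND-36 has no named covariates under any reading, the trigger has no criterion, and the imbalance rule cannot reach the care-use and symptom-day rows.

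**Conclusion.** The point holds as a minor weakness in pre-specification. It is not an error that invalidates any result. Table 2 fixes the three covariates for SNOT-22 only. RAND-36 is left to an undefined trigger that also contradicts the primary row, and five further outcomes have no route to adjustment.

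The cost is modest: intervals that could be 2.5% to 5.1% narrower if the covariates explain 5% to 10% of variance, and an avoidable choice made after seeing data on whether RAND-36 is adjusted. The precision figures rest on the assumed R², and the trigger frequencies on an assumed p-value rule with independent covariates. The textual finding depends on neither. It ranks below any defect in the primary analysis.

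**What to change.** - In Methods for additional analyses, delete the imbalance trigger. This also removes the conflict with the primary row.
- In Table 2, give the RAND-36 row the same unconditional covariates as the primary row: age group, sex and allergy.
- For visits, episodes, sick days, antibiotic courses and symptomatic days, estimate the difference in means from a linear model with treatment and the same three covariates, using robust standard errors. The reported quantity remains a difference in means with its 95% interval. Show the unadjusted difference alongside.
- State that the proportion benefiting is left unadjusted by intention, if that is so.

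The cost is a few lines of SAP wording and one list of model terms. No new data are needed, because the primary model already uses all three covariates. The change should be dated before anyone sees outcome data by arm.

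### Sex and age subgroup effects are to be compared, with a predicted direction, but no treatment-by-subgroup interaction or interval for the difference is specified

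*SAP*

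**What the plan says.** The SAP section on additional analyses announces its scope: "We plan to conduct two subgroup analyses". For sex, "we will compare the estimates for difference between the mean SNOT-22 scores between the ESS and control groups both in males and females". For age: "Secondly, we will do the same analysis in participants aged ≤ 50 and > 50 years of age". It then commits to a direction for both factors: "We anticipate that the treatment effect will be larger among both females and younger participants".

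Elsewhere in the SAP, sex and age group appear only as adjustment variables. Table 2 lists them for the primary outcome: "estimate for difference between means with 95% CI (adjusted age (≤ 50 vs. > 50 years), sex and allergy status". The additional-analyses section lists them again for use if the groups are imbalanced at baseline. The interval promised in the section on primary and secondary outcomes ("The estimate for difference between the means will be calculated with 95% confidence intervals") is for the contrast between surgery and control. It is not for a contrast between two such contrasts.

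**The concern.** To say that surgery helps women more than men is to make a claim about a difference of differences. The SAP fixes the factors, the cut-point and the expected direction, but stops short of the quantity that would address the expectation. No interaction term, contrast of subgroup effects or interval for that contrast is named.

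An analyst who followed the text exactly could print one estimate for each stratum, note which is larger, and stop. With a direction already declared, a gap that happens to fall that way invites the statement that the expectation was borne out, even though its uncertainty was never reported. At stake is the credibility of any statement on who benefits more from surgery. The overall comparison is not at stake.

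**Working it through.** **What the documents supply.** The SAP gives no sample size, power, standard deviation or subgroup size, so it has no figure to reproduce. The whole SAP was read for an interaction term or a contrast between subgroup effects, and neither appears. The rest is an illustration on assumed inputs.

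**Assumptions.** The true effect is the same in both strata. Residual variance and allocation ratio are the same in both. Tests are two-sided at 5%. Overall power is 80% or 90%. One stratum holds a share p of participants, with p = 0.50, 0.35 or 0.30.

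**Step 1: overall effect in units of its standard error.** Effect/SE = 1.96 + 0.84 = 2.80 at 80% power, and 1.96 + 1.28 = 3.24 at 90%.

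**Step 2: standard error of the gap.** The strata are disjoint, so their standard errors are SE/√p and SE/√(1−p), where SE is the overall one. Hence

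SE(gap) = SE × √(1/p + 1/(1−p)) = SE / √(p(1−p)).

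The ratio SE(gap)/SE is 2.00, 2.10 and 2.18 for the three values of p. Dividing by 2.80 or 3.24 gives the SD of the gap as a fraction of the overall effect.

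**Step 3: chance gaps in the predicted direction.** With no true gap, P(gap ≥ k × effect) = 1 − Φ(k / SD), for k = 0.5 and k = 1.

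| Overall power | p | SD(gap)/effect | P(gap ≥ half the effect) | P(gap ≥ whole effect) |
|---|---|---|---|---|
| 80% | 0.50 | 0.714 | 0.242 | 0.081 |
| 80% | 0.35 | 0.748 | 0.252 | 0.091 |
| 80% | 0.30 | 0.779 | 0.260 | 0.100 |
| 90% | 0.50 | 0.617 | 0.209 | 0.053 |
| 90% | 0.35 | 0.647 | 0.220 | 0.061 |
| 90% | 0.30 | 0.673 | 0.229 | 0.069 |

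A simulation of 2,000,000 trials per setting gave 0.2415, 0.2520 and 0.2604 for the half-effect gap at 80% power, and 0.2088, 0.2197 and 0.2286 at 90%.

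**Step 4: what an interaction interval would do.** With no true gap, a 95% CI for the interaction excludes zero in one given direction in 2.5% of trials.

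**Step 5: what it could detect.** If the true interaction were as large as the overall effect, power at 80% overall power is about Φ(2.80/ratio − 1.96), which gives 0.288, 0.267 and 0.250 for the three splits. At an 80:20 split the SE ratio rises to 2.5 and the power falls to about 20%.

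**The case against.** The strongest reply is that the SAP already names the right things to set against each other. It compares effect estimates across strata, not stratum p-values, so it does not plan the classic subgroup error. Its general approach is estimation with 95% intervals. If that carries over to the strata, a reader can approximate the uncertainty of the gap from two disjoint intervals. The subgroups are only two, specified in advance with a direction, and placed among additional analyses with no decision rule attached. The interaction intervals would be too wide to settle much.

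Most of this is fair, and it limits the weight of the point. It is also true that the percentages are not like for like. The 24–26% counts gaps above half the effect, whereas the 2.5% counts gaps above 1.96 standard errors of the gap. At 80% power that second threshold is 1.96 × 0.714 = 1.40 to 1.96 × 0.779 = 1.53 times the overall effect. The figures show how easily a noticeable gap arises by chance. They do not show how often these authors would claim effect modification.

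What does not stand is that nothing is missing. The SAP has its own section on subgroup method, so this is not something left to a protocol. That a reader can derive the uncertainty does not oblige the authors to report it or to rely on it. Low power is a reason to show the wide interval beside the two estimates.

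**Conclusion.** The concern holds as a minor one. The SAP states a directional expectation of effect modification and gives a method that can be followed in full without estimating the uncertainty of the difference in effects.

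Under a uniform true effect and splits from 50:50 to 30:70, a gap of at least half the overall effect in the expected direction would arise by chance in 24–26% of trials per factor at 80% overall power, and in 21–23% at 90%. A gap as large as the whole effect would arise in 8–10% and 5–7%. Power, subgroup shares and both thresholds are assumed; the SAP sets none. That the contrast is unspecified does not depend on them. Neither the primary conclusion nor any secondary outcome is affected.

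**What to change.** Specify that the six-month SNOT-22 analysis of covariance, with baseline SNOT-22 as a covariate, will be fitted in all participants with a treatment × sex term and, in a separate model, a treatment × age-group term (≤ 50 vs > 50). Keep the matching main effect in each model, whether or not baseline imbalance is seen. Table 2 already lists both factors as adjustment terms. Report each interaction estimate with its 95% CI beside the two subgroup effects. Base any statement on effect modification on that interaction alone, labelled exploratory. A p-value is not needed.

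The cost is two sentences of SAP wording and one extra term in each of two models, with no new data. The drawback is imprecision: the interaction SE is about 2.0 to 2.2 times the overall SE. At 80% overall power, there is only 25–29% power for an interaction as large as the overall effect. The intervals are therefore unlikely to settle either expectation.
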